15.3 Sample Size Assumptions

In the DETECT IV trial, the primary objective is to estimate treatment efficacy in patients with HER2-negative metastatic breast cancer and persisting exclusively HER2-negative circulating tumor cells; treatment efficacy will be assessed by the CTC clearance rate in patients treated with everolimus/ribociclib combined with endocrine therapy (everolimus/ribociclib cohort) or by progression-free survival (PFS) in patients treated with eribulin (eribulin cohort). There is no statistical hypothesis underlying the primary analysis.

The following assumptions were made regarding the sample size of patients available for the DETECT IV trial:

- anticipated number of at least 2000 patients with HER2-negative metastatic breast cancer that are to be screened for CTCs in DETECT IV and the related DETECT III trial (which focuses on patients with HER2-negative primary tumor and HER2-positive circulating tumor cells)
- evidence of CTCs (≥ 1) in 65% of patients with metastatic breast cancer (conservative estimate based on Botteri et al. 2010, Fehm et al. 2010, Pierga et al. 2012)
- evidence of exclusively HER2-negative CTCs in 70% of CTC-positive patients (conservative estimate based

on experience from the related DETECT III trial)
Based on these assumptions, the screening will result in about 910 patients with HER2-negative metastatic breast cancer and exclusively HER2-negative CTCs.

Everolimus/ribociclib cohort:

Assuming that 70% of breast cancer patients have a hormone-receptor positive primary tumor and 75% of these patients have postmenopausal status, there will be about 480 postmenopausal patients with hormone-receptor positive, HER2-negative metastatic breast cancer and persisting exclusively HER2-negative CTCs. Based on experience from the related DETECT III trial, a considerable proportion of these patients is expected to fulfill not all of the inclusion criteria, to meet some of the exclusion criteria, or to have an indication for chemotherapy, thus prohibiting the inclusion in the everolimus/ribociclib cohort. We estimate that only about 180 of the 480 patients with hormone-receptor positive, HER2-negative metastatic breast cancer and persisting exclusively HER2-negative CTCs can indeed be included in the everolimus/ribociclib cohort of the DETECT IV trial.

It is assumed that the CTC clearance rate in the everolimus/ribociclib group of our study is in a range similar to that reported in the clinical trial NCT00898014 ("Blood Levels of Tumor Cells in Predicting Response in Patients Receiving First-Line Chemotherapy for Stage IV Breast Cancer"), which showed a CTC clearance rate of 54% after treatment with standard chemo- or endocrine therapy. The anticipated sample size of 160 patients for this study (total of 180 patients enrolled, 90 patients treated with everolimus, 90 patients treated with ribociclib, about 10% loss to follow-up assumed), will then produce a 95% confidence interval for CTC clearance rate with a width of about 23% both for the 80 patients treated with everolimus and the 80 patients treated with ribociclib. Thus, the expected sample size of 160 patients in the everolimus/ribociclib cohort of this study will allow to estimate CTC clearance rate with a reasonable level of precision both for the first 90 patients recruited to the DIVa study that are treated with everolimus and the subsequent 90 patients recruited to the DIVa study that are treated with ribociclib.

An important secondary objective for the everolimus/ribociclib cohort of the DETECT IV trial is the assessment of the dynamic of CTCs by longitudinal comparisons of CTC counts before during and after treatment and the evaluation of the prognostic value of different measures of CTC dynamics. Based on published studies that used a threshold of ≥ 5 CTCs, it is planned to compare PFS between patients that had ≥ 5 CTCs at baseline (start of treatment, T1) and ≥ 5 CTCs at the time of first radiological tumor evaluation after 12 weeks (T2) and patients that had ≥ 5 CTCs at T1 and < 5 CTCs at T2. Assuming that a total of 160 CTC-positive patients can be enrolled and that 68% of all CTC-positive patients have ≥ 5 CTCs (Fehm et al. 2010, Pierga et al. 2012), 109 patients are expected to have levels of CTCs ≥ 5 at T1. With this sample size, we can detect a 39-40% decreased hazard of progression or death for the group of patients with CTCs decreasing from ≥ 5 CTCs at T1 to < 5 CTCs at T2 as compared to the group of patients with CTCs remaining above the threshold level of ≥ 5 CTCs at T2 (assuming the median PFS being in the range of 5.0 and 10.0 months for this group) with a power of 80% (one-sided test with Type I error of 5%). Please note that this analysis refers to a secondary endpoint and thus has explorative character only.

Eribulin cohort:

Assuming that 30% of breast cancer patients have a hormone-receptor negative primary tumor, there will be about 270 patients with triple-negative metastatic breast cancer and persisting exclusively HER2-negative CTCs. In addition, it is estimated that about 20% of all hormone-receptor positive patients have an indication for chemotherapy, resulting in a total of about 390 patients eligible for the eribulin cohort of the DETECT IV trial. Given that this patient cohort (triple-negative or hormone-receptor positive with indication for chemotherapy) is likely to have a worse general health status as compared to the everolimus/ribociclib cohort, a considerable proportion of these patients is expected to fulfill not all of the inclusion criteria, to meet some of the exclusion criteria, or to have other additional comorbidities that prevent the inclusion in the eribulin cohort. If we very conservatively estimate that only about a third of the patients can indeed be included, there will be about 120 patients available that can be recruited in the eribulin cohort of the DETECT IV trial.

It is assumed that the PFS obtained in the eribulin group of our study is in a range similar to that reported in the EMBRACE trial for the Eribulin group (n = 508, median PFS = 3.7 months, 95% confidence interval 3.3 – 3.9 months). With a sample size of 108 patients for this study (total of about 120 patients enrolled, 10% loss to follow-up assumed), a two-sided 95% confidence interval for median PFS with a width of about 1.3 – 1.5 months will be obtained, thus providing an estimate for median PFS with a reasonable precision.

15.4 Safety Analysis

The assessment of safety will be based mainly on the frequency of adverse events. Other safety data (e.g. laboratory values, vital signs, and special tests) will be considered as appropriate. For all safety analyses, the safety set will be used. A safety analysis will be performed by the coordinating investigator and the DSMB after recruitment of 15 patients. Steps will be taken to preserve data confidentiality and to ensure the scientific integrity of the ongoing study. The safety analysis will be conducted on all patients who received at least one dose of the study treatment. Recruitment will not be suspended while this safety analysis is undertaken, except if the stopping thresholds specified above (cf. Premature Discontinuation) are exceeded or on recommendation of the safety review committee (DSMB) for extenuating circumstances (e.g. delay in data retrieval or analysis, emerging unforeseen safety concerns). Every effort will be made to minimize the time from the analysis cut-off date to data retrieval, analysis, and safety review decision. In case of unexpected toxicity the advisory board and the DSMB will be informed and give their advisory vote. Based on the recommendations of this team, a protocol amendment may be implemented to modify dose or study procedures. The safety review is not limited to these adverse events for which stopping rules are established; in the event that other safety concerns are identified, the study could also be closed. All SAEs which are reported to the Sponsor as required by the protocol will be reviewed during this safety analysis. In addition to this safety analysis of the first cohort, ongoing individual events will be reviewed on an ongoing basis, according to routine protocol and pharmacovigilance procedures.

16 **PUBLICATION POLICY**

The results of this study will be published. The responsibility is with the coordinating investigator.

17 **ETHICAL, REGULATORY AND ADMINISTRATIVE ISSUES**

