The main purpose of this multicenter, open-label, single-arm study is to collect efficacy and safety data for the combination of ribociclib with various endocrine therapy regimens (exemestane, letrozole, anastrozole, fulvestrant) in a broader patient population as compared to the MonaLEEs-a-2 trial, and to provide access to ribociclib to patients who are without satisfactory treatment alternatives until ribociclib is approved for this indication. If the study succeeds in proving efficacy of the combined treatment with ribociclib and endocrine therapies, new options for the treatment of hormone-receptor positive MBC can be established.

These data will complement the data of using everolimus in combination with endocrine treatment in the same indication, which were acquired in a first cohort within the Detect IV study. Both primary, as well as secondary endpoints will be compared in terms of a cohort analysis between the two cohorts.

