8.4.3.1 Management of specific toxicities

Neutropenia

The neutropenia observed was reversible and not cumulative; the mean time to nadir was 13 days and the mean time to recovery from severe neutropenia (< 500/ μ l) was 8 days. Neutrophil counts of < 500/ μ l that lasted for more than 7 days occurred in 13% of breast cancer patients treated with eribulin. Neutropenia resulted in discontinuation in < 1% of patients receiving eribulin.

Severe neutropenia may be managed by the use of G-CSF or equivalent at the physician's discretion in accordance with relevant guidelines. 18% of breast cancer patients treated in a phase 3 study with eribulin received G-CSF.

Peripheral neuropathy

In the 827 breast cancer patients the most common adverse reaction resulting in discontinuation of treatment with eribulin was peripheral neuropathy (4%). The median time to Grade 2 peripheral neuropathy was 85 days (post 4 cycles). Development of Grade 3 or 4 peripheral neuropathy occurred in 7% of eribulin treated breast cancer patients. In clinical trials, patients with pre-existing neuropathy were as likely to develop new or worsening symptoms as those who entered the study without the condition. In patients with pre-existing Grade 1 or 2 peripheral neuropathy the frequency of treatment-emergent Grade 3 peripheral neuropathy was 10%.

In case of Neuropathy > grade 2 treatment with eribulin should be withheld until recovery to grade 0-2. Continue therapy with a reduced dose of 1 dose level.

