13.4 Premature Discontinuation of the Entire Study

The sponsor, coordinating investigator and the competent authorities may discontinue or terminate the entire study for the following reasons:

- Identification of a safety risk for the clinical trial participants
- Identification of problems with the trial design
- Non-compliance with the principals of GCP
- Insufficient recruitment of trial participants
- Financial problems

In consultation with the DSMB and the principle investigator the study should be discontinued by the sponsor, represented by [name]. [name], due to safety concerns if any of the following reasons are present:

If due to unexpected events the continuation of the study is not acceptable (ethical, medical or pharmaceutical legal aspects). This will be particularly the case,

- If any grade 4 toxicity occurs in > 20 % of the patients.
- If febrile neutropenia (defined as grade 3 or 4 neutropenia + fever > 38.5 C°) occurs in > 20 % of the patients.
- If grade 4 neutropenia occurs in > 20 % of the patients.
- If an unexpected amount of SUSARs occurs.
- If hand-foot-syndrome grade 4 occurs in > 30 % of the patients.

In the event of study termination, steps will be taken to ensure subjects transition smoothly off study, and if the risk/benefit profile is deemed to be appropriate, subject may continue to receive study treatments at the discretion of the investigator.

All investigators and the sponsor must immediately be informed about the discontinuation or premature termination. The principal investigator at each study site must notify the local competent authority within 15 days after premature termination. The sponsor is to notify the competent authority and the competent ethics committee within the same time interval.

Furthermore, all clinical trial participants must be informed immediately about discontinuation or premature termination. The responsible investigators must ensure that the clinical trial participants are treated and followed up appropriately. Date and time of the last application of the investigational medicinal product as well as date and reason for the discontinuation or premature termination are to be documented in the participants' medical records and on the eCRFs.

In case of permanent discontinuation, all study materials must be sent to the sponsor.

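### The one scheduled aggregate safety analysis (15 patients) cannot include anyone on ribociclib, and the stopping percentages in 13.4 have no drug-specific denominator

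*Protocol*

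**What the plan says.** Section 15.4 schedules one aggregate safety review during the trial: "A safety analysis will be performed by the coordinating investigator and the DSMB after recruitment of 15 patients". It names no cohort or drug for the 15, later describes the review as that of the first cohort, and states no repeat. Beyond it, 15.4 provides for continuing review of individual events. Section 15.2 states that no interim analysis is planned.

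Section 15.3 fixes the order of treatment within DIVa: "the first 90 patients recruited to the DIVa study that are treated with everolimus and the subsequent 90 patients recruited to the DIVa study" are the two groups, the second of them being "the subsequent 90 patients recruited to the DIVa study that are treated with ribociclib". Section 2.7.2 agrees. It says of the everolimus data that they are ones "which were acquired in a first cohort within the Detect IV study". The planned sizes are "total of 180 patients enrolled, 90 patients treated with everolimus, 90 patients treated with ribociclib, about 10% loss to follow-up assumed" for DIVa, and for DIVb "there will be about 120 patients available that can be recruited in the eribulin cohort of the DETECT IV trial".

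Section 13.4 lists the stopping limits under a heading on discontinuing the entire study. The limit is more than 20% for any grade 4 toxicity, for febrile neutropenia and for grade 4 neutropenia, and more than 30% for grade 4 hand-foot syndrome. A typical line is: "If grade 4 neutropenia occurs in > 20 % of the patients". None of them names a drug, a cohort or a time of evaluation. Section 15.4 refers back to these limits as grounds for suspending recruitment during the safety analysis.

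**The concern.** The trial gives three drugs with different toxicity to three groups, one of which starts only after another is full. A single review at 15 patients suits a trial in which those 15 represent what follows. Here they cannot represent the 90 ribociclib patients.

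The limits in 13.4 would be the natural backstop, but they are not tied to a drug. If the denominator is everyone recruited, ribociclib patients are first measured against at least 90 patients who never received the drug. A rate that would exceed the limit within the ribociclib group can then stay below it. What is at stake is whether the protocol's only numerical safety rule works for one of its three drugs.

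**Working it through.** **Nothing to reproduce.** The protocol derives neither the 15 nor the 20% and 30%. The cohort sizes used below are consistent with its own loss-to-follow-up assumption: 180 × 0.9 = 162 (stated as 160) and 120 × 0.9 = 108 (as stated).

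**Inputs.** Everolimus 90, ribociclib 90, eribulin 120, total 300 (15.3). Limit 20% (13.4). Review at 15 recruited patients (15.4).

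**Step 1: ribociclib patients at the scheduled review.** Ribociclib starts after DIVa patient 90. At 15 recruited patients, whatever the mix of everolimus and eribulin, the number on ribociclib is 0.

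**Step 2: early dilution.** Suppose all of the first 15 ribociclib patients have the event and no earlier patient does. With *k* eribulin patients already enrolled, the pooled rate is 15/(90 + 15 + *k*).
- *k* = 0: 15/105 = 14.3%. This is the maximum, and it is also the figure if only DIVa is pooled.
- *k* = 60 (assumed): 15/165 = 9.1%.

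To exceed 20%, at least 23 ribociclib patients, all affected, are needed with *k* = 0 (23/113 = 20.4%), or 38 with *k* = 60 (38/188 = 20.2%).

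**Step 3: dilution at full size.** Pooled rate = (90·p_eve + 90·p_ribo + 120·p_eri)/300. It exceeds 20% when p_ribo > (60 − 90·p_eve − 120·p_eri)/90. The background rates are assumptions:

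| p_eve | p_eri | p_ribo needed to exceed 20% pooled |
|---|---|---|
| 0 | 0 | 66.7% (60 of 90 does not exceed) |
| 1% | 5% | 59% |
| 1% | 10% | 52% |
| 5% | 15% | 42% |
| 0 | 22% | (60 − 26.4)/90 = 37% |
| 0 | 31% | (60 − 37.2)/90 = 25% |

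If only DIVa is pooled, with no everolimus events, the figure is 0.20 × 180/90 = 40%.

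**Step 4: what a within-drug rule would do.** More than 20% of 15 means 4 or more. P(X ≥ 4), X ~ Bin(15, p), is 0.70 at a true 30% and 0.91 at 40%. On all 90 ribociclib patients (19 or more events), it is 0.98 at 30%. By contrast, the pooled count (more than 60 of 300) crosses with probability below 0.001 at a true ribociclib rate of 30%, if everolimus is at 1% and eribulin at 10% (simulation, 400,000 draws).

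A look at 15 is coarse in the other direction too. At the 15.0% rate of grade 4 events (50 of 334) in the phase III ribociclib plus letrozole trial (Table 11), the chance of 4 or more in 15 is 0.18.

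**Step 5: the grade 4 neutropenia limit and eribulin.** Section 8.4.3.1 says that neutrophil counts below 500/µl "that lasted for more than 7 days occurred in 13% of breast cancer patients treated with eribulin", so grade 4 is at least 13%. Table 25 in 8.4.3 gives grade 3 or 4 neutropenia in 48.3%, so grade 4 is at most that. At 13%, P(X ≥ 4 of 15) = 0.12. Grade 4 exceeds 20% only if fewer than 0.13/0.20 = 65% of affected patients pass 7 days, and the protocol does not give that share. Under assumed shares of 60% and exp(−7/8) = 42%, grade 4 would be 22% and 31%, and the chance of 4 or more of 15 eribulin patients 0.43 and 0.73.

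**The case against.** **Pooling is inferred.** Section 13.4 never says that the three drugs are combined. This is right. The defect in the text is that no drug denominator and no time of evaluation are fixed. Pooling is the literal reading of a percentage of patients under an entire-study heading.

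**Other safeguards exist.** A reader might infer that ribociclib receives no cumulative safety review at all. The protocol does not support that. Section 11.4 requires annual safety reports and reporting of a clinically important rise in the rate of an expected serious reaction. Section 15.4 lets the study be closed for concerns outside the listed limits, the list in 13.4 is not exhaustive and acts in consultation with the DSMB, and DSMB procedures are set separately (17.12). These points stand and lessen the gap. None of them schedules a look at ribociclib patients.

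**The 67% is an extreme.** A reader might also infer that the rule is nearly blind to any one drug. That holds only if the other drugs have almost no events of the same kind. For neutropenia, eribulin will contribute events, and the ribociclib rate needed falls accordingly (Step 3).

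**Eribulin neutropenia.** A third tempting inference is that the protocol's own eribulin figures already put grade 4 neutropenia above 20%. They do not. A mean recovery of 8 days is compatible with most episodes lasting beyond 7 days, which would leave the total near 13%. The documents support only 13% to 48.3%.

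**Conclusion.** The point holds in two parts.

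- **Timing.** The only scheduled aggregate safety analysis during the trial contains no ribociclib patient. This needs no assumption beyond the treatment order in 15.3 and 2.7.2. The assignment sections 8.2.1.3 and 8.3.1.3 give no order.
- **Denominator.** Without one by drug, the literal reading of 13.4 dilutes a one-drug signal. The rate is at most 14.3% when all of the first 15 ribociclib patients and no one earlier are affected. At full size the ribociclib rate needed to exceed 20% is 67% with no events elsewhere, 42–59% with assumed rates of 1–5% on everolimus and 5–15% on eribulin, and about 25–37% if eribulin runs at an assumed 31–22% with none on everolimus.

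The existing safeguards reduce the consequence but do not replace a scheduled look. The eribulin neutropenia question is separate and weaker: the limit should be checked against the protocol's own data, but no contradiction is shown.

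**What to change.** 1. In 15.4, state that the 15-patient safety analysis is repeated for the first 15 treated patients in each drug cohort, in particular ribociclib. For everolimus this may only mean recording a review already done.
2. In 13.4, state that each percentage is also computed within drug cohort and when it is evaluated. State also whether a crossing in one cohort leads to review or discontinuation of that cohort or of the whole study. Without this, a within-drug percentage under an entire-study heading could let one cohort stop all three.
3. Separately, the sponsor and DSMB should check the grade 4 neutropenia limit against the eribulin data in 8.4.3 and 8.4.3.1, and record the chance of crossing it at 15 patients over the plausible range (about 12% at a rate of 13%, more at higher rates).

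No threshold value is proposed here. The cost is amendment wording and two extra DSMB tabulations from data already in the eCRF.

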17.1 Regulatory Issues

This study is conducted in compliance with the Declaration of Helsinki (1996), the GCP-Guidelines of the International Conference on Harmonization and applicable German Drug Law.

17.2 Institution Eligibility for Participation

The sponsor acquires information on the potential study site including:

- The potential principal investigator's interest in study participation
- His general experience in the conduct of clinical trials and his experience in similar studies (number of trials performed, number of patients attended in clinical trials)
- Previous audits and inspections
- Suitability of the site facility for study purposes with special regard to radiology
- Emergency equipment, accessibility of the emergency unit of a hospital

17.3 Favorable Opinion of the Competent Ethics Committee and Official Study Approval

On behalf of the sponsor the coordinating investigator will take care, that a favorable opinion of the competent ethics committee on study conduct and approval of the study by the competent authority is obtained. No patient can be included before both have been granted.

Contact data:

Bundesinstitut für Arzneimittel und Medizinprodukte (BfArM)
Probandenkontakttelefon: Frau [name]
[name]
[name]
[contact] //
Stichwort „Fachgebiet Klinische Prüfung / Inspektionen“

17.4 Informed Consent

Patients are only requested to participate in the study, if they suffer from metastasizing breast cancer, if their primary tumor and/or a biopsy from a metastatic site was examined and found to be HER2-negative, and if there is the indication to initiate either a standard endocrine or chemotherapy. Since such patients are expected to be under extreme emotional stress they are intended not to be unduly bothered with detailed information on the study before HER2 status on CTC is known. Therefore informed consent is obtained in two steps. At first patients are asked to consent in blood sampling for CTC count and assessment of HER2 status on CTC (patient information and consent form – part 1). If HER2 status on CTC is negative, their informed consent in study participation is requested (patient information and consent form – part 2). In addition, when both consents have been obtained, patients are also requested to consent in blood sampling for translational medical investigations (patient information and consent form – part 3).

Before signing a consent form, patients are informed about the study orally and in writing. Oral information is to be given by an investigator or by a health professional member of the panel and must include the information given in the respective information leaflets used for written information (patient information – parts 1 to 3). Patients are given ample opportunity to enquire details of the trial and discuss all questions they have. They are left sufficient time to decide on whether to give their consent or not.

The consent forms must be personally signed and dated by the patient and by the investigator who conducted the informed consent discussion. The signed consent forms are retained as part of the trial files. A copy of the consent forms and copy of the information leaflets used are left to the patient. Patient's general practitioner will be informed in case the patient agrees to this procedure.

Before the first informed consent has been obtained no study specific procedure may be carried out. Thereafter only blood sampling for CTC count and assessment of HER2 status is allowed. Further study specific procedures may only be carried out after the second informed consent has been given. Blood samplings for translational medical investigations will only take place if informed consent to these additional examinations is obtained (part 3). If a patient objects, no blood sample will be taken for this purpose, but may nevertheless participate in the study.

The written informed consent forms and any other written information to be provided to patients are revised whenever important new information becomes available that may be relevant to the patient's consent. The sponsor obtains the competent ethics committee's favorable opinion on any revised written informed consent form or and written information material in advance of use. The investigator informs patients already included in a timely manner if new information becomes available that may be relevant to their willingness to continue participation. The communication of this information is documented. In case of monitoring, audits and inspections the medical confidentiality might be revoked.

